## **5.2 Exclusion Criteria**

### **Yes/No (Response of “yes” = patient ineligible)**

**5.2.1**  Is currently participating and receiving study therapy or has participated in a study of an investigational agent and received study therapy or used an investigational device within 2 weeks of the first dose of treatment.

**5.2.2**  Has a diagnosis of immunodeficiency or receiving steroid therapy of any other form of immunosuppressive therapy within 7 days prior to first dose of trial treatment. Subjects who receive daily steroid replacement therapy serve as an exception to this rule. Daily prednisone at doses of 5 to 7.5 mg (or hydrocortisone equivalent doses) is an example of replacement therapy.

**5.2.3**  Has a known history of active TB (Bacillus Tuberculosis).

**5.2.4**  Hypersensitivity to pembrolizumab or any of its excipients.

**5.2.5**  Has had a prior anti-cancer monoclonal antibody (mAb) within 4 weeks prior to study Day 1 or who has not recovered (i.e.,  $\leq$  Grade 1 or at baseline) from adverse events due to agents administered more than 4 weeks earlier.

**5.2.6**  Has had prior chemotherapy, targeted small molecule therapy, or radiation therapy within 2 weeks prior to study Day 1 or who has not recovered (i.e.,  $\leq$  Grade 1 or at baseline) from adverse events due to a previously administered agent. Note: Subjects with  $\leq$  Grade 2 neuropathy are an exception to this criterion and may qualify for the study. Note: If subject received major surgery, they must have recovered adequately from the toxicity and/or complications from the intervention prior to starting therapy. Patients receiving hormone manipulation (e.g. tamoxifen, aromatase inhibitors, LHRH agonist, etc.) for reasons other than treatment of metastatic breast cancer may continue this treatment at the discretion of the investigator.

**5.2.7**  Has a known additional malignancy that is progressing or requires active treatment. Exceptions include basal cell carcinoma of the skin or squamous cell carcinoma of the skin that has undergone potentially curative therapy or in situ cervical cancer. Patients on long-term adjuvant therapy with no evidence of disease are not excluded if felt appropriate by investigator.

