### **7.7.2 Prohibited Concomitant Medications**

Subjects are prohibited from receiving the following therapies during the Screening and Treatment Phase (including retreatment for post-complete response relapse) of this trial:

- Antineoplastic systemic chemotherapy or biological therapy. Hormonal therapies or other long-term adjuvant therapies may be approved after discussion with the principal investigator.
- Immunotherapy not specified in this protocol
- Chemotherapy not specified in this protocol
- Investigational agents other than pembrolizumab
- Radiation therapy
  - Note: Radiation therapy to a symptomatic solitary lesion or to the brain may be allowed at the investigator's discretion.
- Live vaccines within 30 days prior to the first dose of trial treatment and while participating in the trial. Examples of live vaccines include, but are not limited to, the following: measles, mumps, rubella, varicella/zoster, yellow fever, rabies, BCG, and typhoid vaccine.
- Systemic glucocorticoids for any purpose other than to modulate symptoms from an event of clinical interest of suspected immunologic etiology. The use of physiologic doses of corticosteroids may be approved after consultation with the study sponsor (principal investigator).

Subjects who, in the assessment by the investigator, require the use of any of the aforementioned treatments for clinical management should be removed from the trial. Subjects may receive other medications that the investigator deems to be medically necessary.

The Exclusion Criteria describes other medications which are prohibited in this trial.

There are no prohibited therapies during the Post-Treatment Follow-up Phase.

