## **7.8 Duration of Therapy**

A subject must be discontinued from the trial for any of the following reasons:

- The subject or legal representative (such as a parent or legal guardian) withdraws consent.
- Radiographic disease progression by irRECIST (progression must be confirmed with follow up scan no less than 4 weeks and no more than 8 weeks after the first scan shows disease progression)
- Unacceptable adverse experiences as described in Section 8.1
- Intercurrent illness that prevents further administration of treatment
- Investigator's decision to withdraw the subject
- The subject has a confirmed positive serum pregnancy test
- Noncompliance with trial treatment or procedure requirements
- The subject is lost to follow-up
- Completed 24 months of uninterrupted treatment with pembrolizumab or 35 administrations of study medication, whichever is later.

*Note: 24 months of study medication is calculated from the date of first dose.*

- Administrative reasons

The End of Treatment and Follow-up visit procedures are listed in Section 9 (Protocol Calendar). After the end of treatment, each subject will be followed for 30 days for adverse event monitoring (serious adverse events will be collected for 90 days after the end of treatment or until a new cancer treatment is started, if sooner). Subjects who discontinue for reasons other than progressive disease will have post-treatment follow-up for disease status until disease progression, initiating a non-study cancer treatment, withdrawing consent or becoming lost to follow-up. After documented disease progression each subject will be followed for overall survival, withdrawal of consent, or the end of the study, whichever occurs first.

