### **8.1 Dose modification and toxicity management guidelines for pembrolizumab**

#### **8.1.1 Dose modification and toxicity management for immune-related AEs associated with Pembrolizumab**

AEs associated with pembrolizumab exposure may represent an immunologic etiology. These immune-related AEs (irAEs) may occur shortly after the first dose or several months after the last dose of pembrolizumab treatment and may affect more than one body system simultaneously. Therefore, early recognition and initiation of treatment is critical to reduce complications. Based on existing clinical trial data, most irAEs were reversible and could be managed with interruptions of pembrolizumab, administration of corticosteroids and/or other supportive care. For suspected irAEs, ensure adequate evaluation to confirm etiology or exclude other causes. Additional procedures or tests such as bronchoscopy, endoscopy, skin biopsy may be included as part of the evaluation. Based on the severity of irAEs, withhold or permanently discontinue pembrolizumab and administer corticosteroids. Dose modification

and toxicity management guidelines for irAEs associated with pembrolizumab are provided in Table 3.

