**Table 3: Dose modification and toxicity management guidelines for immune-related AEs associated with Pembrolizumab.**

General instructions:				
Immune-related AEs	Grade CTCAE v4	Action taken with pembro	irAE managements	Monitor and follow-up
Pneumonitis	Grade 2	Withhold	Administer corticosteroids (initial dose of 1-2 mg/kg prednisone or equivalent) followed by taper	
 
Monitor participants for signs and symptoms of pneumonitis
 
Evaluate participants with suspected pneumonitis with radiographic imaging and initiate corticosteroid treatment
 
Add prophylactic antibiotics for opportunistic infections
 

	Grade 3 or 4, or recurrent Grade 2	Permanently discontinue		
Diarrhea / Colitis	Grade 2 or 3	Withhold	Administer corticosteroids (initial dose of 1-2 mg/kg prednisone or equivalent) followed by taper	
 
Monitor participants for signs and symptoms of enterocolitis (ie, diarrhea, abdominal pain, blood or mucus in stool with or without fever) and of bowel perforation (ie, peritoneal signs and ileus).
 
Participants with <math>\geq</math> Grade 2 diarrhea suspecting colitis should consider GI consultation and performing endoscopy to rule out colitis.
 
Participants with diarrhea/colitis should be advised to drink liberal quantities of clear fluids. If sufficient oral fluid intake is not feasible, fluid and electrolytes should be substituted via IV infusion.
 

	Grade 4	Permanently discontinue		
AST / ALT elevation or Increased bilirubin	Grade 2	Withhold	Administer corticosteroids (initial dose of 0.5- 1 mg/kg prednisone or equivalent) followed by taper	Monitor with liver function tests (consider weekly or more frequently until liver enzyme value returned to baseline or is stable)

	Grade 3 or 4	Permanently discontinue	Administer corticosteroids (initial dose of 1-2 mg/kg prednisone or equivalent) followed by taper	
Type 1 diabetes mellitus (T1DM) or Hyperglycemia	Newly onset T1DM or Grade 3 or 4 hyperglycemia associated with evidence of $\beta$ -cell failure	Withhold	
 
Initiate insulin replacement therapy for participants with T1DM
 
Administer anti-hyperglycemic in participants with hyperglycemia
 
	Monitor participants for hyperglycemia or other signs and symptoms of diabetes.

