Hypophysitis	Grade 2	Withhold	Administer corticosteroids and initiate hormonal replacements as clinically indicated.	Monitor for signs and symptoms of hypophysitis (including hypopituitarism and adrenal insufficiency)
	Grade 3 or 4	Withhold or permanently discontinue 	Withhold or permanently discontinue 	
Hyperthyroidism	Grade 2	Continue	Treat with non-selective beta-blockers (eg, propranolol) or thionamides as appropriate	Monitor for signs and symptoms of thyroid disorders.
	Grade 3 or 4	Withhold or permanently discontinue 	Withhold or permanently discontinue 	
Hypothyroidism	Grade 2-4	Continue	Initiate thyroid replacement hormones (eg, levothyroxine or liothyroinine) per standard of care	Monitor for signs and symptoms of thyroid disorders.
Nephritis and Renal dysfunction	Grade 2	Withhold	Administer corticosteroids (prednisone 1-2 mg/kg or equivalent) followed by taper.	Monitor changes of renal function
	Grade 3 or 4	Permanently discontinue	Permanently discontinue	
Myocarditis	Grade 1 or 2	Withhold	Based on severity of AE administer corticosteroids	Ensure adequate evaluation to confirm etiology and/or exclude other causes
	Grade 3 or 4	Permanently discontinue	Permanently discontinue	
All other immune-related AEs	Intolerable/ persistent Grade 2	Withhold	Based on type and severity of	Ensure adequate evaluation to confirm etiology and/or exclude other causes

	Grade 3	Withhold or discontinue based on the type of event. Events that require discontinuation include and not limited to: Gullain-Barre Syndrome, encephalitis	AE administer corticosteroids	
	Grade 4 or recurrent Grade 3	Permanently discontinue		

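### The steroid exception in Section 7.7.2 is tied to a term whose only list omits most of the immune-related events that Table 3 treats with steroids while pembrolizumab is merely withheld

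*Combined protocol and SAP*

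**What the plan says.** Section 7.7.2 lists what is prohibited during screening and treatment. The steroid entry reads "Systemic glucocorticoids for any purpose other than to modulate symptoms from an event of clinical interest of suspected immunologic etiology". The same entry lets physiologic doses be approved once the principal investigator has been consulted. After the list comes a consequence: subjects who, in the investigator's judgement, "require the use of any of the aforementioned treatments for clinical management should be removed from the trial".

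Section 16.8 describes events of clinical interest as a selection of events attributed to pembrolizumab, then lists those for this trial after the word *include*. There are two:

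- an overdose with neither symptoms nor abnormal laboratory results;
- AST or ALT at least 3 times the upper limit of normal, with total bilirubin at least 2 times and alkaline phosphatase below 2 times that limit.

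Section 8.1.1 says that most immune-related adverse events "could be managed with interruptions of pembrolizumab, administration of corticosteroids and/or other supportive care". Table 3 then sets, by event and grade, whether pembrolizumab is withheld or stopped for good and whether steroids are given. For pneumonitis and colitis the instruction is "Administer corticosteroids (initial dose of 1-2 mg/kg prednisone or equivalent) followed by taper"; for Grade 2 nephritis it is "Administer corticosteroids (prednisone 1-2 mg/kg or equivalent) followed by taper".

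Section 7.8, which lists the reasons for mandatory discontinuation, handles toxicity through the entry "Unacceptable adverse experiences as described in Section 8.1".

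**The concern.** Two operative rules can apply to the same patient and give different answers. Someone with a first Grade 2 pneumonitis is, under Table 3, given steroids and held off drug. Under the wording of Section 7.7.2, the same patient is taking a prohibited medicine unless pneumonitis counts as an event of clinical interest, and Section 16.8 does not list it.

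At stake is continued access to study drug for patients whose toxicity the protocol otherwise regards as manageable, and consistency between investigators in a multi-site trial. One site could remove a patient whom another would hold and restart. That would bear on drug continuation and on discontinuations for adverse events, which belong to the safety and tolerability objective (Section 1.2.4).

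**Working it through.** The plan gives no figure to reproduce, so the check compares the texts and counts rows.

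**Step 1: what the exception covers if Section 16.8 defines the term.** The overdose entry excludes symptoms by definition, so there is nothing for a steroid to modulate. That leaves the liver laboratory pattern. The other pointer to a definition, in Section 7.7.1, leads to Section 7.2, which covers drug supply and defines no such event.

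**Step 2: Table 3 rows that direct corticosteroids with pembrolizumab only withheld, compared with that list.**

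| Table 3 row | Grade | Steroid instruction | On the 16.8 list? |
|---|---|---|---|
| Pneumonitis | 2 | 1-2 mg/kg prednisone or equivalent | No |
| Diarrhea/colitis | 2, 3 | 1-2 mg/kg prednisone or equivalent | No |
| Nephritis | 2 | 1-2 mg/kg prednisone or equivalent | No |
| Myocarditis | 1, 2 | By severity, no dose given | No |
| All other immune-related events | Intolerable or persistent 2 | By type and severity, no dose given | No |

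Named event-grade pairs: 1 (pneumonitis) + 2 (colitis) + 1 (nephritis) + 2 (myocarditis) = 6, plus the catch-all row.

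**Step 3: rows left out of the count.**

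- Grade 2 liver events may meet the laboratory pattern and so fall inside the exception.
- Steroids for hypophysitis may be physiologic replacement.
- Grade 3 events in the catch-all row may be held or stopped depending on the event.
- Where Table 3 requires permanent discontinuation, the two rules do not differ over study drug.

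**Step 4: does the physiologic-dose allowance close the gap?** No. Section 7.7.2 does not define the term. The nearest guide is the eligibility example in Section 5.2.2: "Daily prednisone at doses of 5 to 7.5 mg (or hydrocortisone equivalent doses) is an example of replacement therapy". Treatment at 1-2 mg/kg is not replacement dosing.

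**Step 5: does Table 3 expect treatment to resume?** It points that way. It reserves permanent discontinuation for Grade 3 or 4 or *recurrent* Grade 2 pneumonitis, which implies that a first Grade 2 episode does not end treatment. The second note to Table 3 provides for resumption after a withheld Grade 3 or 4 endocrinopathy.

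**Step 6: is there a rule of precedence?** No sentence says that Table 3 prevails over Section 7.7.2, or that immune-related adverse events as a class are events of clinical interest.

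**The case against.** The best case against the point is that nobody would read Section 7.7.2 this way. The literal reading nearly empties the exception. The qualifier about immunologic origin fits immune-related events and makes no sense for an overdose. Section 7.7.2 does not refer to Section 16.8, whose list is introduced by a word that leaves it open. A graded, event-specific table would normally govern a general medication list. Section 7.8 sends toxicity to Section 8.1 and does not name prohibited medication as a reason for discontinuation. Section 7.7 words discontinuation as possible, not mandatory, and leaves the last word on supportive therapy with the investigator or the patient's own physician. The removal sentence itself says *should* and depends on the investigator's assessment.

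Most of this stands. It settles the intent and keeps the point minor. It does not withdraw the removal sentence, and Section 7.8 also allows discontinuation on the investigator's decision, so a literal reader still has a route to remove the patient.

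Two stronger inferences fail. A reader might conclude that the protocol denies steroids to these patients; Sections 7.7 and 7.7.1 protect necessary treatment, and Table 3 orders it. A reader might also conclude that the sensible reading turns every immune-related event into a reportable event of clinical interest. Whether a steroid is permitted and whether an event is reportable are separate questions, and the first can be settled without touching the Section 16.8 list.

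**Conclusion.** The point holds as a minor wording conflict between operative patient-management rules. It covers six named event-grade pairs and one catch-all row, for which Table 3 directs steroids with drug withheld and the wording of Section 7.7.2, taken with the Section 16.8 list, calls for removal. The consequence is a risk of unnecessary or inconsistent removal. It depends on someone applying Section 7.7.2 literally and treating the two listed events as the whole meaning of the term. The documents do not show that this happened, and they give no rate of steroid use, so the number of patients cannot be estimated.

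A reader might infer that the response decision in Sections 11.3 and 12 is biased. The documents do not support that. They give no basis for how many patients would be removed or when. Section 7.8 also keeps patients who stop for reasons other than progression in follow-up for disease status, until progression, a new cancer treatment, withdrawal of consent or loss to follow-up.

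**What to change.** In Section 7.7.2, replace the event-of-clinical-interest phrase in the steroid entry with: *adverse event of known or suspected immune-related etiology managed under Section 8.1/Table 3*. Keep *suspected*, because Section 8.1.1 and the pneumonitis row of Table 3 call for action before the cause is confirmed. Add one sentence stating that the removal rule does not apply to steroids given for such events, and that withholding or discontinuation then follows Table 3. Leave the Section 16.8 list and its reporting times unchanged.

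The cost is one phrase and one sentence at the next amendment, with no added procedures, visits or patients.

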## **7.8 Duration of Therapy**

A subject must be discontinued from the trial for any of the following reasons:

- The subject or legal representative (such as a parent or legal guardian) withdraws consent.
- Radiographic disease progression by irRECIST (progression must be confirmed with follow up scan no less than 4 weeks and no more than 8 weeks after the first scan shows disease progression)
- Unacceptable adverse experiences as described in Section 8.1
- Intercurrent illness that prevents further administration of treatment
- Investigator's decision to withdraw the subject
- The subject has a confirmed positive serum pregnancy test
- Noncompliance with trial treatment or procedure requirements
- The subject is lost to follow-up
- Completed 24 months of uninterrupted treatment with pembrolizumab or 35 administrations of study medication, whichever is later.

*Note: 24 months of study medication is calculated from the date of first dose.*

- Administrative reasons

The End of Treatment and Follow-up visit procedures are listed in Section 9 (Protocol Calendar). After the end of treatment, each subject will be followed for 30 days for adverse event monitoring (serious adverse events will be collected for 90 days after the end of treatment or until a new cancer treatment is started, if sooner). Subjects who discontinue for reasons other than progressive disease will have post-treatment follow-up for disease status until disease progression, initiating a non-study cancer treatment, withdrawing consent or becoming lost to follow-up. After documented disease progression each subject will be followed for overall survival, withdrawal of consent, or the end of the study, whichever occurs first.

## **8 TOXICITIES AND DOSAGE MODIFICATION**

This study will utilize the CTCAE (NCI Common Terminology Criteria for Adverse Events) Version 4.0 for adverse event and serious adverse event reporting.

### **8.1 Dose modification and toxicity management guidelines for pembrolizumab**

#### **8.1.1 Dose modification and toxicity management for immune-related AEs associated with Pembrolizumab**

AEs associated with pembrolizumab exposure may represent an immunologic etiology. These immune-related AEs (irAEs) may occur shortly after the first dose or several months after the last dose of pembrolizumab treatment and may affect more than one body system simultaneously. Therefore, early recognition and initiation of treatment is critical to reduce complications. Based on existing clinical trial data, most irAEs were reversible and could be managed with interruptions of pembrolizumab, administration of corticosteroids and/or other supportive care. For suspected irAEs, ensure adequate evaluation to confirm etiology or exclude other causes. Additional procedures or tests such as bronchoscopy, endoscopy, skin biopsy may be included as part of the evaluation. Based on the severity of irAEs, withhold or permanently discontinue pembrolizumab and administer corticosteroids. Dose modification

and toxicity management guidelines for irAEs associated with pembrolizumab are provided in Table 3.

**Table 3: Dose modification and toxicity management guidelines for immune-related AEs associated with Pembrolizumab.**

General instructions:				
Immune-related AEs	Grade CTCAE v4	Action taken with pembro	irAE managements	Monitor and follow-up
Pneumonitis	Grade 2	Withhold	Administer corticosteroids (initial dose of 1-2 mg/kg prednisone or equivalent) followed by taper	
 
Monitor participants for signs and symptoms of pneumonitis
 
Evaluate participants with suspected pneumonitis with radiographic imaging and initiate corticosteroid treatment
 
Add prophylactic antibiotics for opportunistic infections
 

	Grade 3 or 4, or recurrent Grade 2	Permanently discontinue		
Diarrhea / Colitis	Grade 2 or 3	Withhold	Administer corticosteroids (initial dose of 1-2 mg/kg prednisone or equivalent) followed by taper	
 
Monitor participants for signs and symptoms of enterocolitis (ie, diarrhea, abdominal pain, blood or mucus in stool with or without fever) and of bowel perforation (ie, peritoneal signs and ileus).
 
Participants with <math>\geq</math> Grade 2 diarrhea suspecting colitis should consider GI consultation and performing endoscopy to rule out colitis.
 
Participants with diarrhea/colitis should be advised to drink liberal quantities of clear fluids. If sufficient oral fluid intake is not feasible, fluid and electrolytes should be substituted via IV infusion.
 

	Grade 4	Permanently discontinue		
AST / ALT elevation or Increased bilirubin	Grade 2	Withhold	Administer corticosteroids (initial dose of 0.5- 1 mg/kg prednisone or equivalent) followed by taper	Monitor with liver function tests (consider weekly or more frequently until liver enzyme value returned to baseline or is stable)

	Grade 3 or 4	Permanently discontinue	Administer corticosteroids (initial dose of 1-2 mg/kg prednisone or equivalent) followed by taper	
Type 1 diabetes mellitus (T1DM) or Hyperglycemia	Newly onset T1DM or Grade 3 or 4 hyperglycemia associated with evidence of $\beta$ -cell failure	Withhold	
 
Initiate insulin replacement therapy for participants with T1DM
 
Administer anti-hyperglycemic in participants with hyperglycemia
 
	Monitor participants for hyperglycemia or other signs and symptoms of diabetes.
Hypophysitis	Grade 2	Withhold	Administer corticosteroids and initiate hormonal replacements as clinically indicated.	Monitor for signs and symptoms of hypophysitis (including hypopituitarism and adrenal insufficiency)
	Grade 3 or 4	Withhold or permanently discontinue 	Withhold or permanently discontinue 	
Hyperthyroidism	Grade 2	Continue	Treat with non-selective beta-blockers (eg, propranolol) or thionamides as appropriate	Monitor for signs and symptoms of thyroid disorders.
	Grade 3 or 4	Withhold or permanently discontinue 	Withhold or permanently discontinue 	
Hypothyroidism	Grade 2-4	Continue	Initiate thyroid replacement hormones (eg, levothyroxine or liothyroinine) per standard of care	Monitor for signs and symptoms of thyroid disorders.
Nephritis and Renal dysfunction	Grade 2	Withhold	Administer corticosteroids (prednisone 1-2 mg/kg or equivalent) followed by taper.	Monitor changes of renal function
	Grade 3 or 4	Permanently discontinue	Permanently discontinue	
Myocarditis	Grade 1 or 2	Withhold	Based on severity of AE administer corticosteroids	Ensure adequate evaluation to confirm etiology and/or exclude other causes
	Grade 3 or 4	Permanently discontinue	Permanently discontinue	
All other immune-related AEs	Intolerable/ persistent Grade 2	Withhold	Based on type and severity of	Ensure adequate evaluation to confirm etiology and/or exclude other causes

	Grade 3	Withhold or discontinue based on the type of event. Events that require discontinuation include and not limited to: Gullain-Barre Syndrome, encephalitis	AE administer corticosteroids	
	Grade 4 or recurrent Grade 3	Permanently discontinue		

